- The verbatim reports of unsolicited AEs will be reviewed by a physician and the signs and symptoms will be coded according to MedDRA. Every verbatim term will be matched with the appropriate Preferred Term. The percentage of subjects with unsolicited AEs occurring within 31-day (Day 0- Day 30) follow-up period after any dose with its exact 95% CI [Clopper, 1934] will be tabulated by group, and by preferred term. Similar tabulation will be done for unsolicited AEs rated as grade 3, for unsolicited AEs with causal relationship to vaccination and AEs/SAEs leading to withdrawal from the study.
- The percentage of subjects who receive concomitant medication and antipyretic medication during the 4-day (Day 0- Day 3) follow-up period and the 31-day follow-up (Day 0 – Day 30) will be tabulated (with exact 95% CI [Clopper, 1934]) after each vaccine dose and overall.
- SAEs reported from first vaccination dose up to study end will be described in detail.
- Withdrawal due to AEs and SAEs following vaccinations will be described in detail.

Handling of missing data:

- For a given subject and the analysis of solicited AEs 4 days post-vaccination, missing or non-evaluable measurements will not be replaced. Therefore, the analysis of the solicited AEs based on the TVC will include only vaccinated subjects and doses with documented safety data (i.e. symptom screen completed).
- For analysis of unsolicited AEs, such as SAEs or AEs by primary Medical Dictionary for Regulatory Activities (MedDRA) term, and for the analysis of concomitant medications, all vaccinated subjects will be considered. Subjects, who do not report the event or the concomitant medication, will be considered as subjects without the event or the concomitant medication, respectively.
- For summaries reporting both solicited and unsolicited AEs, all vaccinated subjects will be considered. Subjects, who do not report the event or the concomitant medication, will be considered as subjects without the event or the concomitant medication, respectively.

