11.2.5. Safety

For analysis of solicited, unsolicited adverse events such as serious adverse events or adverse events by primary MedDRA term, and for the analysis of concomitant medications, all vaccinated subjects will be considered. Subjects who did not report the event or the concomitant medication will be considered as subjects without the event or the concomitant medication respectively.

For a given subject and the analysis of solicited adverse events within 4 days post-vaccination, missing or non-evaluable measurements will not be replaced. Therefore, the analysis of the solicited adverse events based on the Total Vaccinated Cohort will include only vaccinated subjects for doses with documented safety data (i.e., symptom screen completed). More specifically the following rules will be used:

- Subjects who documented the absence of a solicited adverse events after one dose will be considered not having that adverse events after that dose.
- Subjects who documented the presence of a solicited symptom and fully or partially recorded daily measurement over the solicited period will be included in the summaries at that dose and classified according to their maximum observed daily recording over the solicited period.
- Subjects who documented the presence of a solicited symptom after one dose without having recorded any daily measurement will be assigned to the lowest intensity category at that dose (i.e., 37.5°C for fever or grade 1 for other symptoms).
- Doses without symptom sheets documented will be excluded.
- The intensity of the following solicited adverse events will be assessed as described in the below table

Table 4 Intensity scales for solicited symptoms in infants less than 6 years of age

Adverse Event	Intensity grade	Parameter
Pain at injection site	0	None
	1	Mild: Minor reaction to touch
	2	Moderate: Cries/protests on touch
	3	Severe: Cries when limb is moved/spontaneously painful
Redness at injection site		Record greatest surface diameter in mm
Swelling at injection site		Record greatest surface diameter in mm
Fever*		Record temperature in °C/°F
Irritability/Fussiness	0	Behaviour as usual
	1	Mild: Crying more than usual/no effect on normal activity
	2	Moderate: Crying more than usual/interferes with normal activity
	3	Severe: Crying that cannot be comforted/prevents normal activity
Drowsiness	0	Behaviour as usual
	1	Mild: Drowsiness easily tolerated
	2	Moderate: Drowsiness that interferes with normal activity

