	3	Severe: Drowsiness that prevents normal activity
Loss of appetite	0	Appetite as usual
	1	Mild: Eating less than usual/no effect on normal activity
	2	Moderate: Eating less than usual/interferes with normal activity
	3	Severe: Not eating at all

*Fever is defined as temperature $\geq 37.5^{\circ}\text{C}$ / 99.5°F for oral, axillary or tympanic route, or $\geq 38.0^{\circ}\text{C}$ / 100.4°F for rectal route. The preferred route for recording temperature in this study will be rectal/axillary.

The maximum intensity of local injection site redness/swelling will be scored at GSK Biologicals as follows:

0	Absent
1	≤ 5 mm
2	> 5 mm and ≤ 20 mm
3	> 20 mm

The maximum intensity of fever (oral, axillary or tympanic route) will be scored at GSK Biologicals as follows:

Grade	Temperature
0	$<37.5^{\circ}\text{C}$
1	$\geq 37.5^{\circ}\text{C}$ to $\leq 38.0^{\circ}\text{C}$
2	$>38.0^{\circ}\text{C}$ to $\leq 39.0^{\circ}\text{C}$
3	$> 39.0^{\circ}\text{C}$

The investigator will assess the maximum intensity that occurred over the duration of the event for all unsolicited AEs (including SAEs) recorded during the study. The assessment will be based on the investigator's clinical judgement.

The intensity should be assigned to one of the following categories:

- 1 (mild) = An AE which is easily tolerated by the subject, causing minimal discomfort and not interfering with everyday activities.
- 2 (moderate) = An AE which is sufficiently discomforting to interfere with normal everyday activities.
- 3 (severe) = An AE which prevents normal, everyday activities (in a young child, such an AE would, for example, prevent attendance at school/kindergarten/a day-care centre and would cause the parent(s)/LAR(s) to seek medical advice.

An AE that is assessed as Grade 3 (severe) should not be confused with a SAE. Grade 3 is a category used for rating the intensity of an event; and both AEs and SAEs can be assessed as Grade 3. An event is defined as 'serious' when it meets one of the pre-defined outcomes as described in Section 8.1.2 in the protocol.

The way the percentage of subjects will be derived will depend on the event analysed (see table below for details). As a result, the N value will differ from one table to another.

Event	N used for deriving % per subject	N used for deriving % per dose
Concomitant vaccination	All subjects with study vaccine administered	All study visits with study vaccine administered

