Solicited general AEs	All subjects with at least one solicited general AE documented as either present or absent (i.e., symptom screen completed)	All study visits with study vaccine administered and with at least one solicited general AE documented as either present or absent (i.e., symptom screen completed)
Solicited local AEs	All subjects with at least one solicited local AE documented as either present or absent (i.e., symptom screen completed)	All study visits with study vaccine administered and with at least one solicited local AE documented as either present or absent (i.e., AE screen completed)
Unsolicited AEs	All subjects with study vaccine administered	All study visits with study vaccine administered
Concomitant medication	All subjects with study vaccine administered	All study visits with study vaccine administered

11.2.6. Number of decimals displayed:

The following decimal description from the decision rules will be used for the demography, immunogenicity and safety/reactogenicity.

Display Table	Parameters	Number of decimal digits
Demographic characteristics	Mean, median age	1
Demographic characteristics	SD (age)	1
Immunogenicity	GMT/GMC	3 for anti-D, anti-T and anti-PRP 2 for Strepto antigens 1 for anti-PT, anti-FHA and anti-PRN, anti-HBs, anti-Polio 1, anti-Polio 2 and anti-Polio 3
Reactogenicity	Mean, Min, Q1, Median, Q3, Max for duration	1
All summaries	% of count, including LL & UL of CI	1

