dTpa Group = This group will consist of infants born to mothers belonging to the dTpa Group in study 116945 [DTPA (BOOSTRIX)-047]. All subjects in this group will receive *Infanrix hexa* co-administered with *Prevenar 13* according to the routine national immunisation schedule.

Control Group: This group will consist of infants born to mothers belonging to the Control group in study 116945 [DTPA (BOOSTRIX)-047]. All subjects in this group will receive *Infanrix hexa* co-administered with *Prevenar 13* according to the routine national immunisation schedule. For each dose and overall/subject:

N= number of subjects with at least 1 documented dose

n(%) = number(percentage) of subjects reporting the symptom at least once

For Overall/dose:

N= number of documented doses

n(%) = number(percentage) of doses followed by at least 1 type of symptom

95%CI= Exact 95% confidence interval; LL = lower limit, UL = upper limit

Related: Symptoms which is assessed by the investigator as related to vaccination

Template 20 Percentage of Unsolicited symptoms experienced by subjects classified by MedDRA Primary System Organ Class and Preferred Term within the 31-day (Days 0-30) after any dose (Total vaccinated cohort)

Primary System Organ Class (CODE)	Preferred Term (CODE)	dTpa Group N =			Control Group N =		
		n*	n	%	n*	n	%
At least 1 symptom							
<each SOC>	<each PT term>						

dTpa Group = This group will consist of infants born to mothers belonging to the dTpa Group in study 116945 [DTPA (BOOSTRIX)-047]. All subjects in this group will receive *Infanrix hexa* co-administered with *Prevenar 13* according to the routine national immunisation schedule.

Control Group: This group will consist of infants born to mothers belonging to the Control group in study 116945 [DTPA (BOOSTRIX)-047]. All subjects in this group will receive *Infanrix hexa* co-administered with *Prevenar 13* according to the routine national immunisation schedule. For each dose and overall/subject:

At least 1 symptom = at least 1 symptom experienced (regardless of the MedDRA Preferred Term)

N = number of subjects with the administered dose

n* = number of events reported

n(%) = number(percentage) of subjects reporting the symptom at least once

95% CI = exact 95% confidence interval; LL = Lower Limit, UL = Upper Limit

Template 21 Number (%) of subjects with serious adverse events from the Day 0 to end of the study (Total Vaccinated cohort)

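### SAP 11.2.5 uses one denominator for all solicited general symptoms and one for all local symptoms, so a blank item on an answered sheet counts as absent; two other SAP rules give different denominators

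*SAP*

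**What the plan says.** The table of denominators in SAP 11.2.5 has one row for solicited general events and one for solicited local events.

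- General, per subject: "All subjects with at least one solicited general AE documented as either present or absent (i.e., symptom screen completed").
- General, per dose: "All study visits with study vaccine administered and with at least one solicited general AE documented as either present or absent".
- Local, per subject: "All subjects with at least one solicited local AE documented as either present or absent (i.e., symptom screen completed").
- Local, per dose: "All study visits with study vaccine administered and with at least one solicited local AE documented as either present or absent".

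The sentence before the table says "As a result, the N value will differ from one table to another". It does not say that N differs between symptoms within a table. The footnotes of Templates 18 and 19 use "N= number of subjects with at least 1 documented dose" for each dose and overall/subject, and the number of documented doses for overall/dose. None of these is symptom-specific.

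On missing data, SAP 6.4.1 (like protocol 10.5) says that "missing or non-evaluable measurements will not be replaced" for solicited events, and carries this out by keeping only doses with documented safety data. SAP 11.2.5 repeats the rule and adds: "Subjects who documented the absence of a solicited adverse events after one dose will be considered not having that adverse events after that dose". It excludes doses with no symptom sheet. It does not say what happens to a single blank item on a sheet that was otherwise answered.

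Two other places bear on the same rates. The opening paragraph of SAP 11.2.5 lists solicited events among those for which all vaccinated subjects are considered and non-reporters count as without the event. SAP 11.2.2 defines incidence per dose as visits with the event among all vaccination visits.

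**The concern.** Take a sheet with drowsiness answered, but neither a yes/no for fever nor a temperature. Under the table it is in N for fever and cannot be in n. In effect it is counted as no fever, although nobody recorded that. This defeats the purpose of not replacing missing values.

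The SAP also offers more than one denominator for the same row: sheets with at least one item answered, all vaccinated subjects (opening paragraph of 11.2.5), or all vaccination visits (11.2.2). A programmer could defend any of them, and the choice moves the reported rate.

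These tables carry the secondary reactogenicity objective. Fever is a reaction that protocol 1.3.1 and 6.6 describe as more frequent when the two study vaccines are given together, so its reported frequency will be read closely.

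**Working it through.** **Plan's own figure.** There is none. The documents give no expected symptom rate, no item-level missingness and no precision target for safety. As a check of the interval method only, exact Clopper-Pearson limits were recomputed for seven of the n = 300 rows of protocol Table 22. All seven agree (for example 70%: 64.5 to 75.1; 95%: 91.9 to 97.2).

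**Inputs.** p = true rate per dose; m = share of returned sheets blank for that symptom, blanks at random. Both are assumed. About 300 sheets per group at one dose follows from the 601 infants in the SAP 6.3.2 schedule table (601/2 = 300.5), taking equal groups.

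**Per dose.** Sheet-level rate = p × (1 − m); symptom-level rate = p. The shift is −p × m, a relative loss of exactly m.

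| p | m = 0 | m = 1% | m = 2% | m = 5% | m = 10% |
|---|---|---|---|---|---|
| 20% | 0 | −0.2 | −0.4 | −1.0 | −2.0 |
| 40% | 0 | −0.4 | −0.8 | −2.0 | −4.0 |
| 60% | 0 | −0.6 | −1.2 | −3.0 | −6.0 |

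(Percentage points. The 95% CI half-width at n = 300 is 4.7 points at p = 20% and 5.7 at 40% or 60%.)

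**Worked example (assumed counts).** 300 sheets, 15 with the fever item blank, 114 fevers. Sheet-level: 114/300 = 38.0% (32.5 to 43.8). Symptom-level: 114/285 = 40.0% (34.3 to 45.9).

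**Overall/subject, three independent doses.** True rate 1 − (1 − p)³; sheet-level rate 1 − [1 − p(1 − m)]³. At p = 40% and m = 5%: 1 − 0.60³ = 78.4% against 1 − 0.62³ = 76.2%. The loss is 2.2 points, or 2.8% in relative terms rather than 5%.

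**Between groups.** Equal m leaves the rate ratio unchanged. At p = 40% in both groups, m = 5% against 2% gives a spurious difference of 40 × (0.95 − 0.98) = −1.2 points, and 10% against 2% gives −3.2.

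**The other rules.** If a share u of sheets is not returned at all, the all-visits definition in SAP 11.2.2 gives p × (1 − u) × (1 − m). The opening paragraph of 11.2.5 likewise counts unreturned sheets as no event. The next paragraph of 11.2.5, SAP 6.4.1 and protocol 10.5 all exclude undocumented doses. In SAP 6.4.1 and protocol 10.5, the non-reporter rule covers unsolicited events, concomitant medication and combined solicited-plus-unsolicited summaries only.

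**The case against.** The strongest reply is that a completed screen may mean one with every item answered, so that m = 0. The SAP's wording does not support this: the table explains a completed screen by the test that at least one item is documented. What does stand is that m may be small in practice. The protocol has diary cards verified with the parents at the next visit and unreturned cards sought, and protocol 11.1 allows queries on eCRF omissions.

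A reader might go further than the documents allow in four ways.

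- *That the rates are biased low as a fact.* This depends on m, which the documents do not give.
- *That temperature is the item usually left blank.* Nothing says so. Redness and swelling also need a measurement, and a fever recorded as present without any reading is kept and placed in the lowest category.
- *That the denominator flatly breaks the no-replacement rule.* The SAP and protocol themselves carry that rule out at sheet level, and the SAP never says that only a documented absence counts. The denominator fits the letter of the rule and defeats its purpose.
- *That Prevenar 13 local rates per dose are heavily understated because visits with Infanrix hexa alone enter N.* The visit wording in 11.2.5 permits this reading. Against it, the Template 18 footnote counts documented doses, and SAP 11.2.2 counts a product's doses as the times it was given. The share of infants on a 2-dose Prevenar 13 course is not stated either. This is an ambiguity to settle, not a demonstrated error.

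It is also fair to say that all analyses are descriptive, that both groups follow the same rule, and that a 2-point shift lies inside the interval half-width of 5.7 points.

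**Conclusion.** The point holds as a conditional one. As written, a blank item on an otherwise answered sheet acts as absent. The per-dose rate is then understated by the blank fraction: 2 points at p = 40% and m = 5%, both assumed, with blanks at random. It is zero if no items are blank, and smaller in relative terms for overall/subject rows (2.8% in the same case). The plainest contradiction needs no assumption about blanks: the opening paragraph of SAP 11.2.5 conflicts with the paragraph that follows it, with SAP 6.4.1 and with protocol 10.5, and SAP 11.2.2 adds another per-dose denominator. The consequence is confined to descriptive secondary reactogenicity rates. The primary immunogenicity endpoints are untouched, and a comparison between groups by rate ratio is distorted only if blanks are more common in one group.

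**What to change.** 1. In the SAP 11.2.5 table and the footnotes of Templates 18 and 19, define N for each symptom as the subjects or doses with that symptom documented present or absent.
2. Report the number missing per symptom, by group and dose.
3. Remove *solicited* from the opening sentence of SAP 11.2.5, so that the non-reporter rule has the scope set in protocol 10.5.
4. Align the incidence-per-dose definition in SAP 11.2.2 with item 1 for solicited symptoms.
5. For the product rows of Template 18, state that N counts only visits at which that product was given and its injection site documented.

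Item 1 corrects the per-dose rows but hardly moves the overall/subject row, because a subject leaves N only if the symptom is blank at every dose. With m = 5% and three doses that share is 0.05³ = 0.0125%, and 76.17% becomes 0.7617/0.999875 = 76.18%. For that row, the counts in item 2 are what let a reader judge the effect.

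The cost is a short SAP edit and minor programming, with no new data. The downside is that N will differ slightly from row to row within a table.

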12. ANNEX 3: STUDY SPECIFIC MOCK TFL

The following drafted study specific mocks will be used.

The data display, title and footnote is for illustration purpose and will be adapted to the study specificity as indicated in the TFL TOC.

These templates were copied from recent studies. Note that there may be few changes between the study specific SAP mock TFL and the final TFLs as editorial/minor changes do not require a SAP amendment.

Template 1 Number of subjects enrolled by center (Total vaccinated cohort)

Center	dTpa Group		Control group		Total	
	n	N	n	N	n	%
PPD						
PPD						
PPD						
PPD						
PPD						
PPD						
PPD						
PPD						
PPD						
PPD						
PPD						
All						

dTpa Group = This group will consist of infants born to mothers belonging to the dTpa Group in study 116945 [DTPA (BOOSTRIX)-047]. All subjects in this group will receive *Infanrix hexa* co-administered with *Prevenar 13* according to the routine national immunisation schedule.

Control Group: This group will consist of infants born to mothers belonging to the Control group in study 116945 [DTPA (BOOSTRIX)-047]. All subjects in this group will receive *Infanrix hexa* co-administered with *Prevenar 13* according to the routine national immunisation schedule.

n = number of subjects included in each group or in total for a given center or for all centers

All = sum of all subjects in each group or in total (sum of all groups)

% = n/All x 100

Template 2 Number of subjects enrolled by country (Total vaccinated cohort)

Country	dTpa Group	Control group	Total	
	n	N	n	%
Australia				
Belgium				
Canada				
Czechia				
Finland				
Italy				
Spain				
All				

dTpa Group = This group will consist of infants born to mothers belonging to the dTpa Group in study 116945 [DTPA (BOOSTRIX)-047]. All subjects in this group will receive *Infanrix hexa* co-administered with *Prevenar 13* according to the routine national immunisation schedule.

Control Group: This group will consist of infants born to mothers belonging to the Control group in study 116945 [DTPA (BOOSTRIX)-047]. All subjects in this group will receive *Infanrix hexa* co-administered with *Prevenar 13* according to the routine national immunisation schedule.

n = number of subjects included in each group or in total for a given country or for all countries

All = sum of all subjects in each group or in total (sum of all groups)

% = $n/\text{All} \times 100$

dTpa Group = This group will consist of infants born to mothers belonging to the dTpa Group in study 116945 [DTPA (BOOSTRIX)-047]. All subjects in this group will receive *Infanrix hexa* co-administered with *Prevenar 13* according to the routine national immunisation schedule.

Control Group: This group will consist of infants born to mothers belonging to the Control group in study 116945 [DTPA (BOOSTRIX)-047]. All subjects in this group will receive *Infanrix hexa* co-administered with *Prevenar 13* according to the routine national immunisation schedule.

N = number of subjects who are still in the study up to the visit

Withdrawn = subject who did not return after the visit

Template 5 Number of subjects enrolled into the study as well as excluded from ATP analyses with reasons for exclusion

Title	Total				dTpa Group			Control Group		
	N	n	s	%	N	n	s	N	n	s
Total enrolled cohort	1200				300			300		
Invalid informed consent or fraud data (code 900)										
Study vaccine dose not administered AT ALL but subject number allocated (code 1030)										
TVC	1200		100	300			300			
Administration of vaccine(s) forbidden in the protocol (code 1040)		2	2			0	0		0	0
Randomisation code broken at the investigator site OR at GSK Safety department (1060)										
Study vaccine dose not administered according to protocol (code 1070)		73	73			23	23		16	16
Vaccine temperature deviation (code 1080)										
Expired vaccine administered (code 1090)		10	11			3	3		1	1
Protocol violation (inclusion/exclusion criteria) (code 2010)		1	1			1	1		0	0
Administration of any medication forbidden by the protocol (code 2040)		1	1			0	0		1	1
Underlying medical condition forbidden by the protocol (code 2050)		1	1			0	0		0	0
Concomitant infection related to the vaccine which may influence immune response (2060)										
Concomitant infection not related to the vaccine which may influence immune response (code 2070)		0	1			0	0		0	1
Noncompliance with vaccination schedule (including wrong and unknown dates) (code 2080)		14	16			6	7		3	4
Noncompliance with blood sampling schedule (including wrong and unknown dates) (code 2090)		12	16			3	5		4	5
Essential serological data missing (code 2100)		87	95			20	22		23	26
Obvious incoherence, abnormal serology evolution or error in data (code 2120)		1	1			0	0		0	0
ATP cohort for analysis of immunogenicity	998		83.2	244			252			

dTpa Group = This group will consist of infants born to mothers belonging to the dTpa Group in study 116945 [DTPA (BOOSTRIX)-047]. All subjects in this group will receive *Infanrix hexa* co-administered with *Prevenar 13* according to the routine national immunisation schedule.

Control Group: This group will consist of infants born to mothers belonging to the Control group in study 116945 [DTPA (BOOSTRIX)-047]. All subjects in this group will receive *Infanrix hexa* co-administered with *Prevenar 13* according to the routine national immunisation schedule.

Note: Subjects may have more than 1 elimination code assigned

n = number of subjects with the elimination code assigned excluding subjects who have been assigned a lower elimination code number

s = number of subjects with the elimination code assigned

% = percentage of subjects in the per protocol set (ATP) relative to the TVC(ES)

Template 6 Deviations from specifications for age and intervals between study visits for subjects vaccinated with *Infanrix hexa* (<2> dose schedule - 1 dose/visit) (Total Vaccinated Cohort)

Group		Age	VAC:1-VAC:2	VAC:2-SER:2
		Protocol	Protocol	Protocol
		from 6 to 14 weeks and 6 days	from 52 to 78 days	from 21 to 48 days
dTpa Group	N			
	n			
	%			
	range			
Control Group	N			
	n			
	%			
	range			

dTpa Group = This group will consist of infants born to mothers belonging to the dTpa Group in study 116945 [DTPA (BOOSTRIX)-047]. All subjects in this group will receive *Infanrix hexa* co-administered with *Prevenar 13* according to the routine national immunisation schedule.

Control Group: This group will consist of infants born to mothers belonging to the Control group in study 116945 [DTPA (BOOSTRIX)-047]. All subjects in this group will receive *Infanrix hexa* co-administered with *Prevenar 13* according to the routine national immunisation schedule.

N = total number of subjects with available results

n(%) = number(percentage) of subjects with results outside of the interval

range = minimum-maximum for age and intervals

VAC:1 = vaccination at visit 1

VAC:2 = vaccination at visit 2

SER:2 = blood sample collected before the first dose and 1 month after the last dose of the primary vaccination course

2 dose schedule = subjects who received 2 dose of *Infanrix hexa* at 2,4 months of age or 3,5 months of age, co-administered with *Prevenar 13* (according to the routine national immunisation schedule of the country).

Template 7 Summary of demographic characteristics (Total vaccinated cohort)

		dTpa Group N =		Control Group N =		Total N =	
Characteristics	Parameters or Categories	Value or n	%	Value or n	%	Value or n	%
Age (week) at vaccination dose: 1	Mean						
	SD						
	Median						
	Q1						
	Q3						
Gender	Female						
	Male						
Geographic Ancestry	African Heritage / African American						
	American Indian or Alaskan Native						
	Asian - Central / South Asian Heritage						
	Asian - East Asian Heritage						
	Asian - Japanese Heritage						
	Asian - South East Asian Heritage						
	Native Hawaiian or Other Pacific Islander						
	White - Arabic / North African Heritage						
	White - Caucasian / European Heritage						
	Other (Hispanic)						
Dose schedule	2 dose schedule						
	3 dose schedule						
Maternal age group	18-24Y						
	25-34Y						
	35-45Y						
Gestational week of foetus at dose 1	27-32W						
	33-36W						

dTpa Group = This group will consist of infants born to mothers belonging to the dTpa Group in study 116945 [DTPA (BOOSTRIX)-047]. All subjects in this group will receive *Infanrix hexa* co-administered with *Prevenar 13* according to the routine national immunisation schedule.

Control Group: This group will consist of infants born to mothers belonging to the Control group in study 116945 [DTPA (BOOSTRIX)-047]. All subjects in this group will receive *Infanrix hexa* co-administered with *Prevenar 13* according to the routine national immunisation schedule.

N = total number of subjects

n(%) = number(percentage) of subjects in a given category

Value = value of the considered parameter

SD = standard deviation

Q1 = Quartile 1

Q2 = Quartile 3

2 dose schedule = subjects who received 2 dose of *Infanrix hexa* at 2,4 months of age or 3,5 months of age, co-administered with *Prevenar 13* (according to the routine national immunisation schedule of the country).

3 dose schedule = subjects who received 3 dose of *Infanrix hexa* at 2,3,4 months of age or 2,4,6 months of age, co-administered with *Prevenar 13*. *Prevenar 13* could be administered as 2-doses or 3-doses primary vaccination schedule (according to the routine national immunisation schedule of the country).

18-24Y = 18-24 years old subjects

25-34Y = 25-34 years old subjects

35-45Y = 35-45 years old subjects

27-32W = 27-32 weeks of gestation of foetus at dose 1

33-36W = 33-36 weeks of gestation of foetus at dose 1

Template 8 Summary of vital signs characteristics (Total Vaccinated Cohort)

		dTpa Group (N = 335)	Control Group (N = 336)	Total (N = 671)
Characteristics	Parameters	Value	Value	Value
Height (cm)	Mean			
	SD			
	Median			
	Q1			
	Q3			
	Unknown			
Weight (kg)	Mean			
	SD			
	Median			
	Q1			
	Q3			
	Unknown			
Head circumference (cm)	Mean			
	SD			
	Median			
	Q1			
	Q3			
	Unknown			
Body mass index in [kg/m ²]	Mean			
	SD			
	Median			
	Q1			
	Q3			
	Unknown			

dTpa Group = This group will consist of infants born to mothers belonging to the dTpa Group in study 116945 [DTPA (BOOSTRIX)-047]. All subjects in this group will receive *Infanrix hexa* co-administered with *Prevenar 13* according to the routine national immunisation schedule.

Control Group: This group will consist of infants born to mothers belonging to the Control group in study 116945 [DTPA (BOOSTRIX)-047]. All subjects in this group will receive *Infanrix hexa* co-administered with *Prevenar 13* according to the routine national immunisation schedule.

N = total number of subjects

Value = value of the considered parameter

SD = standard deviation

Height (cm) = height expressed in centimeters

Weight (kg) = weight expressed in kilograms

Head circumference(cm) = head circumference expressed in centimeters.

Body mass index in [kg/m²] = body mass index expressed in kilograms per meter square

SD = standard deviation

Q1 = Quartile 1

Q2 = Quartile 3

Template 9 Study population (TVC)

Study population (Total vaccinated cohort)		
Number of subjects	dTpa group	Control group
Planned, N	225	225
Randomised, N (Total Vaccinated Cohort)	224	227
Completed, n (%)	224 (100)	227 (100)
Demographics	dTpa group	Control group
N (Total Vaccinated Cohort)	224	227
Females: Males	97:127	115:112
Mean Age, weeks (SD)	8.8 (1.1)	8.8 (1.1)
Median Age, weeks (minimum, maximum)	9 (7, 11)	9 (7, 11)
Most frequent race: Asian - East Asian Heritage, n (%)	224 (100)	226 (99.6)

dTpa Group = This group will consist of infants born to mothers belonging to the dTpa Group in study 116945 [DTPA (BOOSTRIX)-047]. All subjects in this group will receive *Infanrix hexa* co-administered with *Prevenar 13* according to the routine national immunisation schedule.

Control Group: This group will consist of infants born to mothers belonging to the Control group in study 116945 [DTPA (BOOSTRIX)-047]. All subjects in this group will receive *Infanrix hexa* co-administered with *Prevenar 13* according to the routine national immunisation schedule.

N = total number of subjects enrolled in the study

n/% = number/percentage of subjects in a given category

SD = Standard Deviation

Mean Age = age calculated from Date of birth to first study vaccination

Template 10 Seropositivity rates and GMCs for anti-PT, anti-FHA and anti-PRN antibodies before the first dose and 1 month after the last dose of the primary vaccination (ATP cohort for immunogenicity)

Antibody	Group	Timing	N	≥ assay cut-off*				GMC		
				n	%	LL	UL	value	95% CI	
								LL	UL	
Anti-PT	dTpa Group	Pre-Pri								
		Post-Pri								
	Control Group	Pre-Pri								
		Post-Pri								
Anti-FHA	dTpa Group	Pre-Pri								
		Post-Pri								
	Control Group	Pre-Pri								
		Post-Pri								
Anti-PRN	dTpa Group	Pre-Pri								
		Post-Pri								
	Control Group	Pre-Pri								
		Post-Pri								

dTpa Group = This group will consist of infants born to mothers belonging to the dTpa Group in study 116945 [DTPA (BOOSTRIX)-047]. All subjects in this group will receive *Infanrix hexa* co-administered with *Prevenar 13* according to the routine national immunisation schedule.

Control Group: This group will consist of infants born to mothers belonging to the Control group in study 116945 [DTPA (BOOSTRIX)-047]. All subjects in this group will receive *Infanrix hexa* co-administered with *Prevenar 13* according to the routine national immunisation schedule.

*Assay cut-off is 2.693 IU/mL for anti- PT, 2.046 IU/mL for anti-FHA and 2.187 IU/mL for anti-PRN

GMC = geometric mean antibody concentration calculated on all subjects

N = number of subjects with available results

n(%)=number(percentage) of subjects with antibody concentrations above the specified cut-off

95% CI = exact 95% confidence interval; LL = Lower Limit, UL = Upper Limit

Pre-Pri = blood sample to be collected before the first dose of the primary vaccination course

Post-Pri = blood sample to be collected 1 month after the last dose of the primary vaccination course

Template 11 Seropositivity, seroprotection and GMC rates for <anti-tetanus> antibodies before the first dose and 1 month after the last dose of the primary vaccination (ATP cohort for immunogenicity)

			≥ assay cut-off*				≥ 0.1 IU/mL				≥ 1.0 IU/mL				GMC			
					95% CI				95% CI				95% CI			95% CI		
Antibody	Group	Timing	N	n	%	LL	UL	n	%	LL	UL	n	%	UL	UL	value	LL	UL
Anti-tetanus	dTpa Group	Pre-Pri																
		Post-Pri																
	Control Group	Pre-Pri																
		Post-Pri																
Anti-diphtheria	dTpa Group	Pre-Pri																
		Post-Pri																
	Control Group	Pre-Pri																
		Post-Pri																

dTpa Group = This group will consist of infants born to mothers belonging to the dTpa Group in study 116945 [DTPA (BOOSTRIX)-047]. All subjects in this group will receive *Infanrix hexa* co-administered with *Prevenar 13* according to the routine national immunisation schedule.

Control Group: This group will consist of infants born to mothers belonging to the Control group in study 116945 [DTPA (BOOSTRIX)-047]. All subjects in this group will receive *Infanrix hexa* co-administered with *Prevenar 13* according to the routine national immunisation schedule.

*Assay cut-off is 0.043 IU/mL for anti-tetanus and 0.057 IU/mL for anti-diphtheria

GMC = geometric mean antibody concentration calculated on all subjects

N = number of subjects with available results

n(%)=number(percentage) of subjects with antibody concentrations above the specified cut-off

95% CI = exact 95% confidence interval; LL = Lower Limit, UL = Upper Limit

Pre-Pri = blood sample to be collected before the first dose of the primary vaccination course

Post-Pri = blood sample to be collected 1 month after the last dose of the primary vaccination course

Template 12 Seroprotection rates for anti-poliovirus type 1,2,3 antibodies before the first dose and 1 month after the last dose of the primary vaccination (ATP cohort for immunogenicity)

Antibody	Group	Timing	N	n	%	≥ 8		GMT			
						95% CI	UL	UL	value	LL	UL
anti-poliovirus type 1	dTpa Group	Pre-Pri									
		Post-Pri									
	Control Group	Pre-Pri									
		Post-Pri									
anti-poliovirus type 2	dTpa Group	Pre-Pri									
		Post-Pri									
	Control Group	Pre-Pri									
		Post-Pri									
anti-poliovirus type 3	dTpa Group	Pre-Pri									
		Post-Pri									
	Control Group	Pre-Pri									
		Post-Pri									

dTpa Group = This group will consist of infants born to mothers belonging to the dTpa Group in study 116945 [DTPA (BOOSTRIX)-047]. All subjects in this group will receive *Infanrix hexa* co-administered with *Prevenar 13* according to the routine national immunisation schedule.

Control Group: This group will consist of infants born to mothers belonging to the Control group in study 116945 [DTPA (BOOSTRIX)-047]. All subjects in this group will receive *Infanrix hexa* co-administered with *Prevenar 13* according to the routine national immunisation schedule.

GMT = geometric mean antibody concentration calculated on all subjects

N = number of subjects with available results

n(%)=number(percentage) of subjects with antibody concentrations above the specified cut-off

95% CI = exact 95% confidence interval; LL = Lower Limit, UL = Upper Limit

Pre-Pri = blood sample to be collected before the first dose of the primary vaccination course

Post-Pri = blood sample to be collected 1 month after the last dose of the primary vaccination course

Template 13 Vaccine responses for anti-PT, anti-FHA and anti-PRN antibody concentration 1 month after the last dose of the primary vaccination course (ATP cohort for immunogenicity)

				Vaccine response			
						95% CI	
Antibody	Group	Pre-Pri* status	N	n	%	LL	UL
anti-PT	dTpa Group	S-					
		S+ (≥cut-off IU/mL)					
		Total					
	Control Group	S-					
		S+ (≥cut-off IU/mL)					
		Total					
anti-FHA	dTpa Group	S-					
		S+ (≥cut-off IU/mL)					
		Total					
	Control Group	S-					
		S+ (≥cut-off IU/mL)					
		Total					
anti-PRN	dTpa Group	S-					
		S+ (≥cut-off IU/mL)					
		Total					
	Control Group	S-					
		S+ (≥cut-off IU/mL)					
		Total					

dTpa Group = This group will consist of infants born to mothers belonging to the dTpa Group in study 116945 [DTPA (BOOSTRIX)-047]. All subjects in this group will receive *Infanrix hexa* co-administered with *Prevenar 13* according to the routine national immunisation schedule.

Control Group: This group will consist of infants born to mothers belonging to the Control group in study 116945 [DTPA (BOOSTRIX)-047]. All subjects in this group will receive *Infanrix hexa* co-administered with *Prevenar 13* according to the routine national immunisation schedule.

S- = Initially seronegative subjects (antibody concentration below assay cut-off for anti-PT, anti-FHA, anti-PRN)

S+ = Initially seropositive (antibody concentration above assay cut-off for anti-PT, anti-FHA, anti-PRN)

